#### 30. PROTOCOL AMENDMENTS

Any significant change in the study requires a protocol amendment. An investigator must not make any changes to the study without IRB/IEC and Sponsor approval except when necessary to eliminate apparent immediate hazards to the subjects. A protocol change intended to eliminate an apparent immediate hazard to subjects may be implemented immediately, but the change must then be documented in an amendment, reported to the

IRB/IEC within 5 working days, and submitted to the appropriate regulatory agency in the required time frame. All protocol amendments must be reviewed and approved by the Sponsor and the investigator.

## 31. QUALITY CONTROL AND ASSURANCE

The Sponsor performs quality control and assurance checks on all clinical studies that it sponsors. Before enrolling any subjects in this study, Sponsor personnel and the investigator review the protocol, the investigator's brochure, the eCRFs and instructions for their completion, the procedure for obtaining informed consent/assent, and the procedure for reporting AEs and SAEs. A qualified representative of the Sponsor will monitor the conduct of the study by visiting the study site and by contacting the study site by telephone, fax, mail, or e-mail. During these study site visits, information recorded in the eCRFs is verified against source documents.

## 32. DIRECT ACCESS, DATA HANDLING, AND RECORD-KEEPING

## 32.1. Investigator

The investigator will permit study-related monitoring, audits, IRB/IEC review, and regulatory inspections by providing direct access to source data and documents.

All information will be recorded on source documents. The subject's medical record is considered to be the source document for the study unless it is information collected specifically for this study and recorded directly in the subject's Subject Diary or in eCRFs. All required data will be recorded in the eCRFs. All eCRF data must be submitted to the Sponsor throughout and at the end of the study. Remote data capture will be used to record and transmit data electronically to the Sponsor.

Central laboratory data will be transmitted directly to the Sponsor. There may be no prior written or electronic record for these data.

If an investigator retires, relocates, or otherwise withdraws from conducting the study, the investigator must notify the Sponsor to agree upon an acceptable storage solution. Regulatory agencies will be notified with the appropriate documentation. An updated Form 1572 will be filed with the Sponsor for any changes in the study personnel reported in the current Form 1572.

#### 32.2. Sponsor

The eCRF data are stored in a database and processed electronically. The Sponsor clinician reviews the data for safety information. The data are reviewed for legibility, completeness, and logical consistency. Automated validation programs identify missing data, out-of-range data, and other data inconsistencies. Requests for data clarification are forwarded to the investigative site for resolution. By participating in this study, the investigator (and their designated staff) accepts responsibility for resolving questions about study data to the best of their ability.

#### 33. SUBJECT INJURY

In general, subject to specific provisions in the Clinical Study Agreement (CSA), if a subject is injured as a direct result of a test article, the Sponsor will pay for reasonable and necessary medical treatment for the injury, to the extent that such expenses are not covered by the subject's medical insurance, a government program, or other responsible third party. If laws or regulations of the locality in which the study is taking place require additional payment of expenses, the Sponsor shall comply with such laws or regulations. Where applicable, the Sponsor has taken specific national insurance.

#### 34. PRESTUDY DOCUMENTATION

The investigator must provide the Sponsor with the following documents BEFORE enrolling any subjects:

- Completed and signed Form 1572.
- All applicable country-specific regulatory forms.
- Current (within 2 years) signed and dated curricula vitae for the investigator, subinvestigators, and other individuals having significant investigator responsibility who are listed on the form 1572 or equivalent, or the clinical study information form.
- Copy of the IRB/IEC approval letter for the protocol and informed consent. All
  advertising, recruitment, and other written information provided to the subject must
  be approved by the IRB/IEC. Written assurance of continuing approval (at least
  annually) as well as a copy of the annual progress report submitted to the IRB/IEC
  must also be provided to the Sponsor.
- Copy of the IRB/IEC-approved informed consent document to be used.
- Where applicable, a list of the IRB/IEC members and their qualifications, and a description of the committee's working procedure.
- Copy of the protocol sign-off page signed by the investigator.
- Fully executed CSA.
- Where applicable, a financial disclosure form.
- A written document containing the name, location, certification number, and date of
  certification of the laboratory to be used for laboratory assays and those of other
  facilities conducting tests. This document should be returned along with the
  statement of investigator form (Form 1572). The Sponsor must be notified if the
  laboratory is changed or if any additional laboratory is to be used.

• List of normal laboratory values and units of measure for all laboratory tests required by the protocol. This is required for each laboratory to be used during the study. The Sponsor must be notified if normal values or units of measurement change.

#### 35. RECORDS RETENTION

The investigator shall retain and preserve 1 copy of all data generated in the course of the study, specifically including but not limited to those defined by GCP as essential, for the longer of (i) 2 years after the last marketing authorization for the study drug has been approved or the Sponsor has discontinued its research with respect to such drug or (ii) such longer period as required by applicable global regulatory requirements. At the end of such period, the investigator shall notify the Sponsor in writing of its intent to destroy all such material. The Sponsor shall have 30 days to respond to the investigator's notice, and the Sponsor shall have a further opportunity to retain such materials at the Sponsor's expense.

#### 36. SAMPLE RETENTION

Samples may be used for purposes related to this research, such as repeat testing is needed. The samples will be stored for up to 15 years after the end of the study and then destroyed. In addition, identifiable samples can be destroyed at any time at the request of the subject.

#### 37. CLINICAL STUDY REPORT

As appropriate, an investigator will be selected to act as the signatory for the clinical study report. This investigator will be selected based on clinical experience and understanding of the product.

#### 38. PUBLICATION OF STUDY RESULTS

## 38.1. Communication of Results by Pfizer

Pfizer fulfills its commitment to publicly disclose clinical trial results through posting the results of studies on www.clinicaltrials.gov (ClinicalTrials.gov), the European Clinical Trials Database (EudraCT), and/or www.pfizer.com, and other public registries in accordance with applicable local laws/regulations.

In all cases, study results are reported by Pfizer in an objective, accurate, balanced, and complete manner and are reported regardless of the outcome of the study or the country in which the study was conducted.

## www.clinicaltrials.gov

Pfizer posts clinical trial US Basic Results on www.clinicaltrials.gov for Pfizer-sponsored interventional studies conducted in patients that evaluate the safety and/or efficacy of a Pfizer product, regardless of the geographical location in which the study is conducted. US Basic Results are submitted for posting within 1 year of the primary completion date for studies in adult populations or within 6 months of the primary completion date for studies in pediatric populations.

*Primary completion* date is defined as the date that the final subject was examined or received an intervention for the purposes of final collection of data for the primary outcome, whether the clinical study concluded according to the prespecified protocol or was terminated.

#### **EudraCT**

Pfizer posts EU Basic Results on EudraCT for all Pfizer-sponsored interventional studies that are in scope of EU requirements. EU Basic Results are submitted for posting within 1 year of the primary completion date for studies in adult populations or within 6 months of the primary completion date for studies in pediatric populations.

## www.pfizer.com

Pfizer posts Public Disclosure Synopses (clinical study report synopses in which any data that could be used to identify individual patients has been removed) on www.pfizer.com for Pfizer-sponsored interventional studies at the same time the US Basic Results document is posted to www.clinicaltrials.gov.

## 38.2. Publications by Investigators

Pfizer supports the exercise of academic freedom and has no objection to publication by principal investigator of the results of the study based on information collected or generated by principal investigator, whether or not the results are favorable to the Pfizer product. However, to ensure against inadvertent disclosure of confidential information or unprotected inventions, the investigator will provide Pfizer an opportunity to review any proposed publication or other type of disclosure of the results of the study (collectively, "Publication") before it is submitted or otherwise disclosed.

The investigator will provide any publication to Pfizer at least 30 days before they are submitted for publication or otherwise disclosed. If any patent action is required to protect intellectual property rights, the investigator agrees to delay the disclosure for a period not to exceed an additional 60 days.

The investigator will, on request, remove any previously undisclosed confidential information before disclosure, except for any study- or Pfizer product-related information necessary to the appropriate scientific presentation or understanding of the study results.

If the study is part of a multicenter study, the investigator agrees that the first publication is to be a joint publication covering all study sites, and that any subsequent publications by the principal investigator will reference that primary publication. However, if a joint manuscript has not been submitted for publication within 12 months of completion or termination of the study at all participating sites, the investigator is free to publish separately, subject to the other requirements of this section.

For all publications relating to the study, the institution will comply with recognized ethical standards concerning publications and authorship, including Section II - "Ethical

Considerations in the Conduct and Reporting of Research" of the Uniform Requirements for Manuscripts Submitted to Biomedical Journals, http://www.icmje.org/index.html#authorship, established by the International Committee of Medical Journal Editors.

Publication of study results is also provided for in the CSA between Pfizer and the institution. In this section entitled Publications by Investigators, the defined terms shall have the meanings given to them in the CSA.

If there is any conflict between the CSA and any Attachments to it, the terms of the CSA control. If there is any conflict between this protocol and the CSA, this protocol will control as to any issue regarding treatment of study subjects, and the CSA will control as to all other issues.

## **40. APPENDICES**

## Appendix 1. Guidelines for On-Demand Treatment With Moroctocog alfa (AF-CC)

Guidelines for On-Demand Treatment With Moroctocog alfa (AF-CC), Based on Current Recommendations for On-Demand Therapy With the Licensed Product  $Xyntha^{\circledast}$ 

Type of Bleeding Episode	FVIII Level Required	Frequency of Doses (hours)/
	(IU/dL or % of normal)	Duration of Therapy (days)
Minor Early hemarthrosis, minor muscle or oral bleeds.	20-40	Repeat infusion every 12 to 24 hours as necessary until resolved for at least 1 day, depending upon the severity of the bleeding episode.
Moderate Bleeding into muscles. Mild head trauma. Bleeding into the oral cavity.	30-60	Repeat infusion every 12 to 24 hours for 3 to 4 days, or until adequate local hemostasis is achieved.
Major Gastrointestinal bleeding. Intracranial, intra-abdominal or intrathoracic bleeding. Fractures.	60-100	Repeat infusion every 8 to 24 hours until bleeding is resolved

APPENDIX C: CHANGES IN THE PLANNED ANALYSES FROM INTERIM	
CSRS	33

OVERVIEW AND SUMMARY OF CHANGES TO PLANNED ANALYSES FOR THE FINAL CSR

OVERVIEW

Version 5.0 of this statistical analysis plan (SAP) incorporates updates resulting from Protocol Amendments 5 (A5) through the current Amendment 10 (A10) (including a 2017 Protocol Administrative Change Letter). Text taken directly from the protocol appears in italics. Major updates include a shortened duration for Segment 1 for the on-demand (OD) cohort to 6 months duration from 12 months (Amendment 7 [A7]), removal of incremental recovery assessment at visit 7 and consequently the analysis of k-value (incremental) recovery over time (A7), and an increase in the upper age for the inclusion criteria from less than 6 years to less than 16 years (A10). The original planned sample sizes and the sample size re-estimation results appear in A10 and are reflected in *italics*.

A summary of changes to planned analyses for the Final clinical study report (CSR) is described in the Summary of Changes Section which immediately follows below. These changes do not appear in the body of the SAP 5.0, as they were determined after the implementation of Protocol Amendment 10. These changes include those that were implemented for either of the 2 Interim CSRs (dated 07 November 2013 and 11 April 2016), which will also be applicable for the final study report. In addition, clarification is provided regarding additional changes to analyses planned for the final study report, as a result of recent communications with the Food and Drug Administration (FDA), dated 28 January 2016 and 27 January 2017.

Two additional appendices have been added to support this SAP:

Appendix B provides a summary of changes in the conduct of the study, as per the ten protocol amendments and is included for background information.

Appendix C provides for reference the Summary of Changes to Planned Analyses implemented for both Interim clinical study reports (from CSR Section 9.8.2 in each report). Some of these changes are also relevant to the Final CSR and are referred to in the Summary of Changes Section which immediately follows below.

SUMMARY OF CHANGES TO PLANNED ANALYSES FOR THE FINAL CSR.

1. The first interim CSR presented safety, efficacy and baseline data for subjects at Site PP separately from data for subjects at other sites, due to serious breaches of GCP compliance by the investigator and study staff at Site PP pertaining to data integrity. As implemented in the second Interim CSR, in the Final CSR, safety, efficacy and baseline summary data will be presented excluding Site PP with the exception of protocol deviations, recovery/pharmacokinetic data, and inhibitor incidence, which include all sites.

- 2. As determined for the second Interim CSR for the study's primary endpoint analysis in the OD cohort only, a linear mixed-effects model with unstructured variance-covariance matrix provides a more robust model for the comparison of annualized bleeding rate (ABR) given the nature of the study data, while still controlling for the same factors as specified in the SAP ANOVA model. This model allows for the inclusion of all intent-to-treat (ITT) subjects with ABR data and also takes into account the correlation between the 2 within-subject measurements of ABR at each segment. Because all enrolled subjects had severe (<1%) hemophilia at baseline (ie, just one level of the factor was present and therefore not informative), hemophilia severity is not included as a factor in the model as planned. In the Final CSR, the estimates of the ABR for each regimen (segment) and for the difference as well as the corresponding two-sided 95% confidence intervals (CIs) will be reported using the linear mixed-effects model described above rather than as described in SAP Section 3.3.1.2.
- 3. As implemented in the second Interim CSR as per FDA Written Response dated 28 January 2016 (CRMTS #10042, BL 125264/1540), supportive analyses will also be performed for the ITT population for the Final CSR. A paired t-test will be used to test the within-subject change in ABR for the subjects who will be evaluated with both OD and routine prophylaxis (RP) dosing during the study. In addition, a one-sided 95% CI for the ratio of the arithmetic means for ABR during RP over the ABR during OD treatment will be calculated. Ogawa's parametric confidence interval for the ratio of two paired means¹ assumes the ABR is bivariate normally distributed for RP and OD treatments and will be calculated using R statistical software (version 3.2.3). If the one-sided 95% upper confidence bound is ≤0.5, then this will confirm that the ABR during RP treatment was at least 50% lower than that observed during OD treatment.
- 4. In accordance with FDA correspondence dated 27 January 2017 (IND 10040/246) stating that a non-inferiority clinical margin M2 of 3 bleeds or fewer per year may be adequate, equivalence between the 2 RP regimens will be declared if the limits of the 90% two-sided confidence interval fall wholly within the interval of (-3, 3) bleeds per year, rather than protocol/SAP specified (-4, 4) (SAP Sections 1.4.2 and 3.3.2.2).
- 5. Per FDA correspondence dated 27 January 2017 (IND 10040/246), incidence rate of inhibitor development will be additionally described by number of prior exposure days at study entry. For this assessment, based on the risk of the inhibitor development according to the number of exposure days, minimally treated patients (MTPs) will include those who had accrued 20 to <50 exposure days to any FVIII replacement product prior to enrollment into Protocol B1831001. Note: Previously treated patients (PTPs) are patients who have received FVIII replacement therapy. Prior to Protocol Amendment 4, PTPs were defined for the purposes of the study as those who had accrued at least 50 exposure days (EDs) to any FVIII replacement product prior to study enrollment. To improve enrollment, in Protocol Amendment 4 (dated 15 September 2009) this number was decreased to at least 20 prior EDs for inclusion in the study. SAP Section 3.4.2.1 refers to Inhibitor Development.

- 6. For the exploratory analysis in RP cohort subjects, to test for the presence of treatment sequence, period and carryover effects, SAP Section 3.3.2.2 states that the ANOVA model will be fitted with terms for treatment sequence (AB or BA), treatment frequency (A or B), period (study segment 1 or 2), carryover and subject nested in treatment sequence. However, this model is overparameterized. Instead, the more appropriate mixed-effect model ABR=sequence period treatment, with subject as a random effect will be used to evaluate the treatment effect. Contrasts will be constructed to test if the carryover effect for each sequence is the same, and if the same, if that carryover effect is equal to zero.
- 7. Protocol Amendment 10 has text in section 15.2 (also appears in SAP Section 2.2) which states that the pharmacokinetic dose will be prepared from a single lot. However, multiple lots were used over the course of this study.
- 8. Protocol Amendment 10 has text in sections 22 and 22.6 (also appears in SAP Section 3) which indicates that both efficacy and safety will be reported separately for the 2 cohorts (OD and RP). However, only efficacy data is presented separately, and safety data is presented for all subjects combined.

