2.4. Data Preparation

The sampling times that will be used in the PK calculation will be the actual sampling time recorded relative to the time of dose administration.

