3.2. Analysis Populations

3.2.1. Intent-to-Treat Populations

The intent-to-treat (ITT) population includes all subjects for whom a legal acceptable representative has signed the informed consent/assent form. Screen failures will not be included in the ITT population. All safety and efficacy analyses will be performed on the ITT population.

The modified Intent-to-Treat (mITT) population is the subset of ITT subjects who received at least one dose of moroctocog alfa (AF-CC). Adverse events and lab data analyses will be additionally performed on the mITT population. Analysis of the incidence of confirmed FVIII inhibitor development will also be performed on the mITT population.

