3.8. Multicenter Handling

Because relatively small numbers of subjects will be enrolled at each site, no test of homogeneity across sites will be performed. Data will be pooled from all sites for analysis.

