APPENDIX C: CHANGES IN THE PLANNED ANALYSES FROM INTERIM CSRS

Changes in the Planned Analyses were described in Section 9.8.2 within each of the 2 interim CSRs for this study.

Interim CSR 1 (dated 07 November 2013), in support of the Pediatric 2013 sBLA

9.8.2 Changes in the Planned Analyses: The analyses reported in here are limited and restricted to descriptive statistics. Safety, efficacy and baseline data for subjects at Site are presented separately from data for subjects at other sites, due to serious breaches of Good Clinical Practice (GCP) compliance by the investigator and study staff at Site pertaining to data integrity. Pharmacokinetic (PK) data are objective and it is believed that interpretation of these data is not compromised by the deficiencies noted at Site PPD The PK data which were collected from subjects from this site are, therefore, presented and included in the summary for the study.

Interim CSR 2 (dated 11 April 2016), in support of the Prophylaxis 2016 sBLA

9.8.2 Changes in the Planned Analyses: The previous interim CSR presented safety, efficacy and baseline data for subjects at Site PP separately from data for subjects at other sites, due to serious breaches of GCP compliance by the investigator and study staff at Site PP pertaining to data integrity. In this second interim CSR, safety, efficacy and baseline summary data are presented excluding Site PP with the exception of protocol deviations, and inhibitor incidence, which include all sites.

As per the SAP Section 3.3, efficacy data on and subsequent to the date of inhibitor development was not to be included in the efficacy analyses. However, with the exception of the following summary tables: CSR Section 14.2, Table 14.2.4.3, Table 14.2.4.4, Table 14.2.5.1, and Table 14.2.5.2, the efficacy summary tables did not exclude bleeds occurring after inhibitor development. (This has been corrected for the Final CSR).

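### Dosed children at one site are left out of the final adverse-event and laboratory summaries but kept in inhibitor incidence and PK, and no all-sites safety summary is planned beside them

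*SAP*

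**What the plan says.** The governing text is Item 1 of the Summary of Changes to Planned Analyses for the Final CSR, at the front of the SAP. The site is handled differently "due to serious breaches of GCP compliance by the investigator and study staff at Site PP pertaining to data integrity". For the final report, "safety, efficacy and baseline summary data will be presented excluding Site PP". Three kinds of result are exempt from this rule and keep the site: "with the exception of protocol deviations, recovery/pharmacokinetic data, and inhibitor incidence, which include all sites".

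Handling has changed over time. "The first interim CSR presented safety, efficacy and baseline data for subjects at Site PP separately from data for subjects at other sites"; the second interim report dropped the site from these summaries, and the final report follows the second.

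SAP Appendix C, in its account of the first interim report, gives the reason for keeping PK: "Pharmacokinetic (PK) data are objective and it is believed that interpretation of these data is not compromised by the deficiencies noted". Neither document gives a reason for keeping the site in inhibitor incidence.

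The SAP body has no site exclusion. Section 3.2.1 states: "All safety and efficacy analyses will be performed on the ITT population". It adds that adverse events, laboratory data and inhibitor incidence are also analysed on the mITT population, meaning everyone who received a dose. Section 3.8 states: "Data will be pooled from all sites for analysis". Item 8 of the Summary of Changes says that safety is presented for all subjects combined. It is about merging the two cohorts and does not mention the site.

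**The concern.** Safety incidence is normally reported on everyone exposed. Here the rule takes a group of treated children out of the numerator and denominator of every adverse-event and laboratory summary, and no companion table puts them back. Unreliable site records are a good reason to protect the efficacy comparison. They are a weaker reason to have no all-exposed safety figure at all, because a reader who wants the event rate in all treated children cannot get it from the planned tables.

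The rule also splits the safety results. Inhibitor incidence covers all sites, while the adverse-event summaries cover all sites but one. The same inhibitor can therefore appear in one table and be absent from another in the same report. With about 80 planned subjects, one or two cases settle what is said about a rare event.

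**Working it through.** The plan states no figure on this point, so there is none to reproduce. The check has three parts.

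**1. Were children at the site exposed?** Yes. Appendix C says PK data from the site's subjects were collected and included. Under Protocol 15.2, the PK assessment consists of a study-drug infusion followed by blood sampling. At least those subjects meet the mITT definition.

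**2. Where would an event at this site be counted?**

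| Event at the site | Inhibitor incidence | Adverse-event summaries | Listings and narratives |
|---|---|---|---|
| Inhibitor confirmed centrally (SAP 3.4.2.1: reported as an SAE) | counted | not counted | listed; narrative |
| Inhibitor report not confirmed centrally (Protocol 17.1: counts as an SAE, not as an inhibitor) | not counted | not counted | listed; narrative as an SAE |
| Any other SAE | not applicable | not counted | listed; narrative |
| Non-serious adverse event | not applicable | not counted | listed |

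The last column follows from SAP 3.4, which lists all safety data after consent, and from SAP Appendix A, which plans narratives for SAEs, deaths, inhibitors, LETE and discontinuations due to adverse events. Neither excludes the site.

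**3. How much could it matter?** The site's subject count *k* is not given, so the following is illustration only. The total *N* is 80 (Protocol section 6; 56 + 24) or 72 (SAP 1.3), both planned numbers.

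Share of subjects left out = *k*/*N*:

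| *k* (assumed) | *N* = 80 | *N* = 72 |
|---|---|---|
| 1 | 1.25% | 1.4% |
| 3 | 3.75% | 4.2% |
| 5 | 6.25% | 6.9% |
| 8 | 10.0% | 11.1% |

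The next table shows the incidence of any event with *x* cases at all sites, and then with an assumed site of 5 removed. Exact 95% limits are Clopper-Pearson: lower = Beta(0.025; *x*, *n* − *x* + 1), upper = Beta(0.975; *x* + 1, *n* − *x*).

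| | All sites | Site removed, no case there | Site removed, one case there |
|---|---|---|---|
| *N* = 80, *x* = 2 | 2/80 = 2.5% (0.3–8.7) | 2/75 = 2.7% (0.3–9.3) | 1/75 = 1.3% (0.0–7.2) |
| *N* = 80, *x* = 1 | 1/80 = 1.25% (0.0–6.8) | 1/75 = 1.3% (0.0–7.2) | 0/75 = 0% (0.0–4.8) |
| *N* = 72, *x* = 2 | 2/72 = 2.8% (0.3–9.7) | 2/67 = 3.0% (0.4–10.4) | 1/67 = 1.5% (0.0–8.0) |

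Exclusion takes subjects out of the denominator as well as the numerator. Incidence falls if the site's event rate is above that of the other sites and rises if it is below. In these rows the change is small when no case arose at the site. When one did, the estimate roughly halves or goes to zero.

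**Retained endpoints.** Inhibitor titre and FVIII:C are assayed at the central laboratory (SAP 3.4.2.1; Protocol 19.1), but the reported results also use site-recorded inputs. Protocol 19.2 gives CL = Dose/AUC∞ and incremental recovery = (C0.5h − C0)/Dose, with Dose in IU/kg. If one subject's recorded IU/kg is wrong by a factor *f*, his clearance is multiplied by *f* and his recovery divided by *f*. The curve is built on "the actual sampling time recorded relative to the time of dose administration" (SAP 2.4). The added breakdown of inhibitor incidence (Item 5) uses prior exposure days at study entry, a history taken at the site.

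**The case against.** The strongest reply is that Item 1 is deliberate and defensible. Adverse events are collected and judged by site staff, so they depend directly on a site's record-keeping. The two retained endpoints depend mainly on central assays. Keeping all sites in inhibitor incidence ensures that no confirmed case is lost. A reason is given for keeping PK, and SAP 2.3.1 screens the PK set further for major violations, adequate sampling, washout, non-bleeding state and absence of an inhibitor. The SAP Overview says the listed changes do not appear in the body, so a mismatch with sections 3.2.1 and 3.8 is a declared override. Safety already had more than one denominator, ITT and mITT. Individual events remain in listings and narratives.

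Most of this stands, and it rules out several stronger readings that a reader might draw:

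- **The retained PK and inhibitor figures rest on suspect records, or exposure at the site is doubtful.** The documents say the breaches concerned data integrity, but not which records were affected. Nothing puts dosing in question.
- **The exclusion understates harm.** It could move incidence either way.
- **The site's events are hidden.** They should appear in listings and, where criteria are met, in narratives.
- **The mismatch with SAP 3.8 is itself an error.** The Overview explains it.

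The reply does not answer the main point. Listings and narratives give no incidence, and central assay of two endpoints does not supply adverse-event summaries for all dosed children. The Overview's explanation also does not cover Item 8, which sits in the same list as Item 1 and describes safety as combining all subjects without mentioning the exclusion.

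**Conclusion.** The point holds as a gap in safety reporting. Under Item 1, the final adverse-event and laboratory summaries leave out children who received study drug. No all-exposed version is planned, and an inhibitor-related event at the site can be counted in one summary and not another, or in none. This is less than the first interim report showed.

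The size and direction are unknown. The shares of 1.25% to 10.0% (*N* = 80) or 1.4% to 11.1% (*N* = 72) rest on assumed site sizes of 1 to 8 and on planned enrolment. The inhibitor illustration also assumes a site of 5 and one or two cases overall. The efficacy exclusion is not in dispute. The question about PK and inhibitor incidence is secondary: site-recorded inputs enter these results, and the documents neither show that those inputs were affected nor plan a check that they were not.

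**What to change.** Keep the efficacy and baseline exclusions as written, and amend Item 1 as follows.

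1. Add treatment-emergent and serious adverse-event summaries, and the laboratory summaries, for all dosed subjects at all sites, beside the site-excluded tables. Showing the site separately, as in the first interim report, would also do. State the number of dosed subjects at the site.
2. As a secondary check, report inhibitor incidence (including the breakdown by prior exposure days) and the PK parameters also without the site.
3. Add one sentence on why inhibitor incidence keeps all sites, and one reconciling Item 1 with Item 8.

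The cost is a few repeat tables from existing programs, with no new data. The drawback is that some summaries appear in two versions, so the report must say beforehand which is the main one.
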